Caregivers will also complete at one-time assessment in REDCap. Caregivers will complete a sociodemographic survey (e.g., age, sex, race/ethnicity, education) and a survey about their loved one's cancer treatments. They will also respond to questions asking about their perception of their loved one's self-efficacy for managing symptoms (i.e., modified Self-efficacy for managing chronic disease scale) as well as their own self-efficacy for helping their loved one manage symptoms (i.e., modified self-efficacy for managing chronic disease scale).

The developed intervention will then be reviewed to N=3-5 AYAs with advanced or recurrent cancer to assist with refining intervention content and study procedures. As with focus group/interview participants, user testers will also complete a one-time assessment. Information obtained from user testers will be used to refine the intervention.

D. Aim 2: Pilot RCT. AYAs with advanced or recurrent cancer (aged 15-29) will complete the baseline assessment electronically via Research Electronic Data Capture (REDCap) prior to randomization. The clinical research coordinator will be present at the baseline assessment to assist participants with using REDCap. Participants will then be randomized by the coordinator to the intervention or education control arm using an allocation ratio of 1.5:1. Randomization will be stratified by age (15-19 vs. 20-29). Age categories were chosen to match contemporary definitions of the developmental periods of older adolescence (15-19) and young adulthood (20-29) and echo the definitions of adolescents and young adults adopted by the National Cancer Institute Surveillance, Epidemiology, and End Results Programs.^{13,14} Follow-up assessments will be completed remotely using REDCap on the participant's own or a study-specific device (iPad). Self-report measures have been formatted for use in REDCap. The coordinator will be available via phone in the event of questions or issues.

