AYAs will complete other self-report measures at each assessment to examine change in treatment targets. Most of the assessment tools have been used with the full age range of the proposed study sample (age 15-29),⁸²⁻⁸⁶ and all tools have been validated for use with those aged >18.⁸⁷⁻⁹³ Symptom severity will be assessed using the Brief Pain Inventory⁹⁴ as well as the PROMIS Computer Adaptive Tests for Depression, Anxiety, and Fatigue. Other intervention targets. The Self-Efficacy for Managing Chronic Disease Scale,⁹⁵ Acceptance and Action Questionnaire-II (AAQ-II),⁸⁸ modified Bulls Eye Values Survey⁹² and FACIT-SP-12 will be administered at each assessment; changes in scores will serve as a validity check to ensure the intervention targeted patients' confidence in their abilities to manage symptoms and important concepts from ACT and MCP. The Self-Efficacy for Managing Chronic Disease Scale⁹⁵ assesses symptom self-efficacy. The AAQ-II assesses acceptance, experiential avoidance and psychological flexibility.⁸⁸ The modified Bulls Eye Values Survey⁹² examines personal values, values attainment, and persistence towards values in the face of barriers. The valuing questionnaire will also be used to assess patient values. The FACIT-SP will be used to assess meaning. Use of intervention strategies. At the post-treatment and follow-up assessment, intervention arm participants will also provide information about the use of strategies presented during the intervention over the last week.

The timeline of study assessments is included, below:

Timing of Study Questionnaires SMILE RCT

	Assessment 1	Assessment 2	Assessment 3
Sociodemographics	X		
Medical/Cancer treatment information	X		
PROMIS Depression CAT	X	X	X
PROMIS Anxiety CAT	X	X	X
PROMIS Fatigue CAT	X	X	X
Brief Pain Inventory	X	X	X
Self-Efficacy for Managing Chronic Disease (6-item)	X	X	X
Acceptance and Action Questionnaire-II (7-item)	X	X	X

Bulls Eye Values Scale	X	X	X
Valuing Questionnaire	X	X	X
Treatment Acceptability Scale (Intervention Only)		X	
STTS-R (Intervention Only)		X	
Open Ended Questions about Intervention (Intervention Only)		X	
Use of Intervention Strategies (Intervention Only)		X	X

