Protection Against Risk. First, if a participant (i.e., AYA with advanced or recurrent cancer or caregiver) endorses psychological distress due to study participation, the PI ([name]) will consult with study Co-Is, Drs. [name], [name], [name], and [name]. Drs. [name] and [name] are licensed clinical psychologists. [name] co-directs and [name] is a member of The Cancer Symptom Management and Support Program, which focuses on conducting clinical research and providing behavioral medicine services to address the psychological,

social, behavioral, and symptom management needs of cancer patients and their families. Additional clinical services provided include psychotherapy, psychological assessment, brief memory and cognitive testing, behavioral weight management, treatment of sleep difficulties, coping skills training for symptom management, treatment of sexual difficulties, and stress management. [name] also holds a position within the Duke Department of Psychiatry and Behavioral Sciences. In addition to conducting funded research within the department, she has a clinical practice within the Duke Faculty Practice in Psychiatry. [name] is a general pediatrician and child and adolescent psychiatrist, Co-Chief of the Division of Child and Family Mental Health and Developmental Neurosciences within the Department of Psychiatry and Behavioral Sciences, and Medical Director of Psychiatry Services for the Duke Cancer Institute. In addition to conducting research to better understand the developmental challenges facing youth with childhood-onset chronic conditions as they grow-up, [name] has an active clinical practice at DUMC. [name] is the Director of the Duke Cancer Patient Support Program, an established psychosocial support program that provides no-cost services and resources to patients and their families throughout their experience with cancer. Drs. [name], [name], [name], and [name] will provide guidance regarding the appropriate course of action in the event that a participant endorses distress associated with study participation.

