The PI is also a licensed clinical psychologist in the Department of Psychiatry and Behavioral Sciences at Duke and a member of the Duke Teen and Young Adult Oncology Program, Duke Cancer Patient Support Program, and Cancer Symptom Management and Support Program. Her involvement in these programs will allow her to readily facilitate appropriate referrals for psychosocial services offered through the DCI (e.g., clinical psychologists and medical family therapists affiliated with the Duke Cancer Patient Support and Cancer Symptom Management and Support Programs) and Duke Department of Psychiatry and Behavioral Sciences. Contact information for the PI will be provided should participants have any questions or concerns. Additionally, the clinical research coordinator will be trained to monitor participants' psychological status and report to the PI if a participant shows signs of experiencing high levels of physical and/or emotional distress that need to be addressed outside the context of the trial. If this is determined to be the case, the clinical research coordinator will work directly with the PI and the participant to move forward in a way that is in the best interest of the participant. No participant will be kept in the trial if he or she is experiencing increased or extreme distress. While the PI, Co-Is, and other study staff members have conducted research in the proposed area and have not encountered participants who experience significant psychological distress as a result of study procedures, we are confident that we have sufficient resources (e.g., access to no-cost psychosocial services through the Duke Cancer Patient Support Program, access to psychiatric care through the Department of Psychiatry and Behavioral Sciences) to assist participants in the event that a participant experiences study-related distress. Our prior research has instead found participation in behavioral symptom management interventions to be associated with benefits to physical health, mood, and quality of life; we believe that the possible significance of study findings outweighs the risk.

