'Display participants' names will be unchecked so that their name is not included in the recording.

Only the meeting host will have permission to record the session.

Costs to the Subject

- Describe and justify any costs that the subject will incur as a result of participation; ordinarily, subjects should not be expected to pay for research without receiving direct benefit.

There are no costs to the subjects.

Data Analysis & Statistical Considerations

- Describe endpoints and power calculations. Provide a detailed description of how study data will be analyzed, including statistical methods used, and how ineligible subjects will be handled and which subjects will be included for analysis. Include planned sample size justification. Provide estimated time to target accrual and accrual rate. Describe interim analysis including plans to stop accrual during monitoring. Phase I studies, include dose escalation schema and criteria for dose escalation with definition of MTD and DLT.

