E. Statistical Considerations. This study aims to develop and pilot a novel psychosocial symptom management intervention for AYA's with advanced or recurrent cancer and is not designed to make conclusions about efficacy without further study.⁹⁶ Sample size estimates are based on pragmatics of recruitment over the study timeframe as well as our ability to obtain sufficient data to understand the experiences of the target population and examine intervention feasibility and acceptability. Information gathered will inform the design of future trials. Based on our past published work^{9,76} using focus groups to develop symptom management interventions, a sample size of N=28 (n=16 AYAs, n=12 caregivers) is sufficient to obtain information to confirm, and, when necessary, adapt proposed intervention content to meet the needs of AYAs with advanced or recurrent cancer. N=40 AYAs will participate in the pilot RCT. The sample size accounts for 20% attrition, which was derived from our prior work (10-15%)^{7,9,10} and attrition rates for AYAs with cancer receiving mHealth interventions (12-21%).⁹⁷⁻⁹⁹ The RCT sample size (intervention: n=24, control: n=16) was derived from published recommendations¹⁰⁰ and our past preparatory work.^{7,11} While Aim 2 focuses on examining distributions of change in outcomes and intervention targets rather than testing statistical significance, a priori power calculations using G-Power¹⁰¹ based on intervention effects seen in our prior work⁷ suggest, after accounting for attrition, we will have ~80% power to detect medium effect sizes (d=0.5; $\alpha=0.05$, two-tailed) with an intervention sample of n=19.

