Aim 1. Focus groups will be transcribed verbatim. Qualitative Description¹⁰²⁻¹⁰⁴ using thematic analysis¹⁰⁵⁻¹⁰⁸ as the methodological approach will be used to identify, analyze and report themes and trends across data. A preliminary code book derived from the focus group interview guides will be developed prior to analysis. Codes will be applied to transcripts using NVivo¹⁰⁹ by two individuals to ensure similar understanding of codes and consistency in judgment.¹⁰⁷ Discrepancies in interpretation of the data or application of codes will be resolved. Codebooks will be updated to add data-driven codes; emerging codes will be applied to previously coded text.¹⁰⁸ Codes will then be sorted into themes/subthemes using an iterative process.¹⁰⁸ A descriptive summary will be produced and used to inform the intervention.¹⁰⁴ Intervention user testers (N=3) will provide oral and written feedback related to intervention content, content presentation, and study procedures to better understand the experience of intervention users; materials and procedures will be refined from this feedback.

Aim 2. Descriptive statistics (e.g., mean, percent) will be used to examine feasibility and acceptability data. Change in outcomes (i.e., symptoms, symptom interference) and intervention targets (e.g., self-efficacy, experiential avoidance) from baseline to post-treatment and post-treatment to 4-week follow-up will be examined using paired t-tests. Effect sizes will be computed for the intervention and control arms using Hedges' g_{av} ,¹¹⁰ associated confidence intervals will be examined. Other analyses. Feasibility, acceptability, and patterns of change in outcomes and intervention targets will be examined by sex using descriptive statistics to examine differences that may be obscured when the data is pooled.¹¹¹ We will also examine session completion rates and account for this as necessary in analyses. Our prior work testing videoconferencing symptom management interventions suggests participants will complete 3.4-3.7 of 4 sessions, with 83-90% completing all sessions.^{6,8,9}

Data & Safety Monitoring

- Summarize safety concerns, and describe the methods to monitor research subjects and their data to ensure their safety, including who will monitor the data, and the frequency of such monitoring. If a data monitoring committee will be used, describe its operation, including stopping rules and frequency of review, and if it is independent of the sponsor (per 45 CFR 46.111(a) (6)).

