All data will be stored on a secure server with multiple backups created regularly. All interactions with study participants will be under the direction of three licensed clinical psychologists ([name], PI; [name], Co-I; [name]. [name], Co-I), a pediatrician and child and adolescent psychiatrist ([name], Co-I), a medical family therapist ([name], Co-I), and an oncologist ([name], Co-I). Audio recordings of sessions will also be obtained and reviewed by [name] to ensure fidelity of intervention delivery and that the study therapist is providing effective, ethical treatment. As a practicing clinical psychologist, the PI has experience with distressed patients with chronic disease. If a participant shows signs of experiencing high levels of physical or emotional distress that need to be addressed outside the context of this trial, the PI will work directly with the participant to move forward in a way that is in the participant's best interest. No participant will be kept in the trial if they are experiencing increased extreme distress. Study staff will be carefully trained to monitor participants' psychological status and report to [name] when emotional distress is identified in a participant. [name] as well as [name] work directly with the Duke Cancer Patient Support Program, which is directed by [name] (Co-I). [name] is also a practicing licensed clinical psychologist and [name] is a practicing child and adolescent psychiatrist within the Department of Psychiatry and Behavioral Sciences at Duke. As such, members of the investigative team are integrated into the psychosocial care programs at DCI and within Duke; they have experience referring cancer patients who are distressed to appropriate psychosocial or psychiatric care. They will use the same resources when making referrals for distressed participants in this study.

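### Participants removed for distress are not guaranteed A2 and A3 assessments, so the paired analysis of distress can lose people because of the outcome it measures

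*Combined protocol and SAP*

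**What the plan says.** Two safety sections carry a removal rule. Risk/Benefit Assessment (Protection Against Risk) says "No participant will be kept in the trial if he or she is experiencing increased or extreme distress". Data & Safety Monitoring says "No participant will be kept in the trial if they are experiencing increased extreme distress". Under the first, either an increase or an extreme level is enough; the second appears to need both. Neither gives a measurable threshold, separates stopping the sessions from leaving the study, or mentions the remaining assessments. Protection Against Risk opens with a consultation step for anyone who "endorses psychological distress due to study participation", but the rule sentences carry no such limit.

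Distress is also an outcome. Study Measures lists the "PROMIS Computer Adaptive Tests for Depression, Anxiety, and Fatigue", and its timetable schedules them at A1, A2 and A3. Section D (Aim 2: Pilot RCT) says "Follow-up assessments will be completed remotely using REDCap", with no provision for people who have been removed.

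Under Aim 2 of E. Statistical Considerations, change "from baseline to post-treatment and post-treatment to 4-week follow-up will be examined using paired t-tests", and Hedges' g_av is computed within each arm. The template prompt for this part asks "how ineligible subjects will be handled and which subjects will be included for analysis". The text names no analysis set and no method for missing scores; its only related provision is to account for session completion where needed. The stated focus of Aim 2 is "examining distributions of change in outcomes and intervention targets rather than testing statistical significance".

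**The concern.** A paired comparison uses only people with both scores. If a participant leaves because distress has risen, and the next score is never taken, the people left in that arm are those who did better. The loss depends on the outcome, so the 20% attrition allowance in the sample size does not protect against it: that allowance preserves numbers, not representativeness.

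What is at stake is the description of change that the pilot passes to later trials, including the contrast between arms in H3 and the count of people who clearly worsened. The feasibility measures would not reveal the problem. An intervention participant removed before session 4 counts as a non-completer without a reason, and controls have no sessions to miss. A score that was never collected cannot be recovered at analysis.

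**Working it through.** **Inputs.** From the plan: 24 intervention and 16 control participants; three assessments; paired tests of A1 to A2 and of A2 to A3. Not in the plan, so assumed: the number removed (k = 1 or 2 per arm), that those removed are not assessed, zero true mean change, normally distributed changes, and a correlation of 0.3, 0.6 or 1.0 between noticed distress and the change in score. The plan has no figure for this bias to reproduce.

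**Step 1: who is lost.** Someone removed before A2 is missing from both comparisons. Someone removed between A2 and A3 is missing only from the second.

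**Step 2: shift in A1 to A2 when removal follows a rise.** If the whole arm's expected change is zero and the k removed have mean worsening m, the remaining n − k have expected mean change −k·m/(n − k). For n = 24, simulation gives these values of m, in SDs of change:

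| Correlation | m, k=1 | Shift, k=1 | m, k=2 | Shift, k=2 |
|---|---|---|---|---|
| 0.3 | 0.58 | −0.58/23 = −0.03 | 0.52 | −2(0.52)/22 = −0.05 |
| 0.6 | 1.17 | −1.17/23 = −0.05 | 1.04 | −2(1.04)/22 = −0.09 |
| 1.0 | 1.95 | −1.95/23 = −0.08 | 1.73 | −2(1.73)/22 = −0.16 |

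Negative means apparent improvement. For n = 16 the simulated shifts at correlations 0.3, 0.6 and 1.0 are −0.03, −0.07 and −0.12 (k=1), and −0.07, −0.13 and −0.22 (k=2). To express these in SDs of the score, multiply by √(2(1 − r)), where r is the correlation between two assessments: 1.18 at r = 0.3, 1.00 at 0.5, 0.77 at 0.7. The plan gives no r.

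**Step 3: against precision.** The simulated 95% CI half-width is about 0.4 SD of change for the arm of 24 and 0.5 for the arm of 16. Every shift above is smaller.

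**Step 4: A2 to A3 after removal before A2.** With equal correlations between assessments, the two successive changes correlate −(1 − r)/(2(1 − r)) = −0.5. With serial decay (r, r, r²) the value is −(1 − r)/2, or −0.25 at r = 0.5. The second change therefore moves the other way. For n = 24, k = 2 and noticed-distress correlation 1.0, it is 0.5 × 0.157 = +0.08 or 0.25 × 0.157 = +0.04. Across the n = 24 cases the range is about +0.01 to +0.08, toward worsening.

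**Step 5: other patterns.**
- Removal between A2 and A3 after a rise leaves A1 to A2 intact and gives A2 to A3 the shifts of Step 2.
- Removal of the two highest baseline scores of 24 shifts A1 to A2 by +0.08 (r = 0.5).
- Random loss of two gives 0.00.
- If removed participants still give A2 and A3, the shift is 0.00.

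**Step 6: the worsening tail.** Of 24, 24 × 0.159 = 3.8 would be expected to worsen by at least 1 SD of change. With two removed after a rise before A2, the analysed set shows 3.2, 2.8 or 1.9 at correlations 0.3, 0.6 and 1.0.

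**Step 7: secondary.** The chance of a nominally significant false A1-to-A2 improvement in the intervention arm rises from 2.5% to 3-7% (k=1) or 4-14% (k=2). The top value needs two removals and perfect correlation.

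**The case against.** The strongest reply is that the rule will rarely be used. Protection Against Risk says the team has not met significant distress caused by study procedures in its earlier research, and both safety sections describe individual handling in the participant's interest. That stands as a reason to expect few removals. It does not close the gap. The trigger in both sections is high physical or emotional distress needing attention beyond the trial, which in advanced or recurrent cancer need not come from the study.

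A second reply is that this is a pilot that disclaims efficacy conclusions, and that the bias is below sampling error. Both are true and limit the consequence. The confidence interval still does not reflect selective loss, and describing change is what Aim 2 sets out to do. Accounting for session completion does not help: it cannot supply an A2 score, and controls have no sessions.

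Three stronger readings are tempting, and the documents support none of them:

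- *Removal always makes an arm look better.* Steps 4 and 5 show shifts in both directions, and the Risk/Benefit wording would allow removal for a level that was extreme but unchanged.
- *The rule favours the intervention arm.* That arm is observed more closely, but the sessions may prevent distress, and one removal moves the smaller control arm more. Which arm is affected more is unknown.
- *The attrition of 10-15% in the team's earlier work implies one or two distress removals.* It gives 24 × 0.10 = 2.4 to 24 × 0.15 = 3.6 losses from all causes; no section attributes any of them to distress.

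**Conclusion.** The point holds as a conditional one and should be fixed. The two thresholds, the silence on A2 and A3 after removal, and the lack of an analysis set or missing-score method are plain in the text. Followed literally, the rule drops people from the distress analysis because of distress.

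The direction depends on when and why a person is removed. The bias toward improvement applies to A1 to A2 when removal before A2 follows a rise, and to A2 to A3 when removal after A2 follows a rise. The sizes in Step 2 rest on the assumed removals, correlations and zero true change, and on those removed not being assessed. A reader might go on to infer that the trial could report a false benefit. The documents do not support that, because the plan says it does not set out to test efficacy. The harm is to the mean change, the effect size and the count of people who worsened. Confidence is medium, because the removal rate is unknown.

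**What to change.** Use one wording in Risk/Benefit Assessment and Data & Safety Monitoring, with the threshold left to the principal investigator and the IRB. It should say that:

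- the participant stops the intervention sessions and is referred for care, and controls are referred in the same way;
- the participant stays in the study and is offered A2 and A3, unless the participant, or the parent or guardian of a minor, withdraws consent or assent.

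Add to Aim 2 of E. Statistical Considerations that:

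- all randomised participants with the scores needed for a comparison are analysed in their assigned arm, whether or not sessions were stopped;
- the number stopped or withdrawn for distress, and whether A2 and A3 were obtained, is reported by arm.

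Optionally, repeat the A1-to-A2 distress change with A2 scores missing after a distress stop set to a range of worsening. This should not be extended to A2 to A3: the starting score may be missing too, and worsening may be the wrong direction.

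The cost is an IRB amendment, a short analysis paragraph and one count table. A2 and A3 are already scheduled, remote and paid at $20 each, so no visit or measure is added. Some distressed participants will still decline, and the offer must stay voluntary. Stopped sessions still count against the target of more than 80% completing all four (19/24 = 79.2%, 20/24 = 83.3%, so at least 20 of 24). The change to the rule helps only participants whose follow-up is still open; the reporting by arm can be added at any time.

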Aim 2: Pilot Randomized Controlled Trial. AYAs with advanced or recurrent cancer (N=40) will be randomized to the intervention or an education control arm using an allocation ratio of 1.5:1. Feasibility of study recruitment (N=40 in 12 months) and participant retention (>80% intervention completion) will be examined along with intervention acceptability. Patterns of change in symptom (i.e., pain, fatigue, distress) severity and interference, self-efficacy for symptom management, and targets of ACT and MCP (e.g., acceptance, experiential avoidance, congruency between values and actions) will be examined. **H2:** Study recruitment and retention will be feasible, and the intervention will be acceptable. **H3:** The intervention arm will evidence improvements in symptom severity and interference, self-efficacy, and targets of ACT and MCP not seen in the control arm.

Background & Significance

- Should support the scientific aims of the research

A. Significance. 1. **Scope of the Problem.** In the last four decades, the incidence of cancer among adolescents and young adults (AYAs; aged 15-29) has increased, and for some cancers (e.g., colorectal cancer, melanoma), has increased more rapidly than for any other age group.⁴³⁻⁴⁵ Improvements in morbidity and mortality outcomes for AYAs have lagged behind both younger pediatric and older adult cancer patients; in fact, AYAs more often present with advanced disease, have more aggressive tumors, and have worse prognosis.¹⁵⁻²¹ Cancer is currently the leading cause of disease-related death among AYAs.⁴⁶ The significant disparity in outcomes for AYAs may stem from a number of age-specific factors that result in decreased access to care and can contribute to delays in diagnosis.⁴⁷ For example, AYAs are more likely to be uninsured or underinsured when compared to younger or older cancer patients.⁴⁸⁻⁵¹ AYAs'

perceptions of invincibility may interfere with attending medical appointments even in the presence of symptoms,⁵² and the relatively low frequency of cancer in this age group may lead medical professionals to attribute an AYA's symptoms to a condition other than cancer.⁴⁹

2. AYAs with advanced cancer have high symptom (e.g., pain, fatigue, emotional distress) burden.^{22,23,53,5}

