- Describe the study, providing details regarding the study intervention (drug, device, physical procedures, manipulation of the subject or the subject's environment, etc.). Discuss justifications for placebo control, discontinuation or delay of standard therapies, and washout periods if applicable. Identify procedures, tests and interventions performed exclusively for research purposes or more frequently than standard of care. Include alternative therapies, concurrent therapies discontinued per protocol, risk benefit ratio, and use of tissue/specimens. Discuss monitoring during washout periods if applicable. Include brief description of follow-up, if any.

A. Study Design. We propose to develop a psychosocial symptom management intervention for AYAs with advanced or recurrent cancer and to examine feasibility, acceptability, and patterns of change in outcomes through a pilot RCT. Intervention development will be guided in part by qualitative data from focus groups with: 1) AYAs with advanced or recurrent cancer (n=6/group, 2 groups), 2) caregivers of AYAs with advanced or recurrent cancer (n=8, one group), and 3) a combined caregiver (n=4) and AYA (n=4) group. The intervention and study procedures will be further refined following review by a second group of patient user testers (N=3-5). User testers will review the patient intervention manual and provide feedback to better understand the experience of users and refine the intervention materials and study procedures. It is anticipated that the developed intervention will include traditional behavioral symptom management approaches commonly used in palliative care settings and techniques from MCP and ACT.

The intervention will then be pilot tested through a small RCT. A new group of AYAs with advanced or recurrent cancer (N=40) will be randomized with an allocation ratio of 1.5:1 to the intervention (n=24) or education control (n=16) arms. Participants will complete assessments at baseline (A1), post-treatment (A2; 6-8 weeks after A1), and 4-weeks post-treatment (A3). We will examine feasibility and acceptability, patterns of change in outcomes (i.e., symptoms, symptom interference) and intervention targets (e.g., self-efficacy, acceptance, experiential avoidance) for the intervention and control arms, and sustainability of effects over time.

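### Sustainability of effects is to be examined, but no baseline-to-follow-up change and no between-arm difference at follow-up is planned; both can be added from data already collected

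*Combined protocol and SAP*

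**What the plan says.** Under Design & Procedures, A. Study Design, assessments are set at "baseline (A1), post-treatment (A2; 6-8 weeks after A1), and 4-weeks post-treatment (A3"). The same paragraph says the study will examine patterns of change "for the intervention and control arms, and sustainability of effects over time". Sustainability is not defined there or elsewhere.

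Under Purpose of the Study, hypothesis H3 is comparative: it expects improvements in symptoms, self-efficacy and "targets of ACT and MCP not seen in the control arm".

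Under Study Measures, "AYAs will complete other self-report measures at each assessment to examine change in treatment targets", so outcomes exist at A1, A2 and A3 in both arms. The Aim 2: Pilot RCT section adds: "Randomization will be stratified by age (15-19 vs. 20-29").

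The analysis itself is in Data Analysis & Statistical Considerations, Aim 2. It names two intervals, A1-A2 and A2-A3. The second appears as "post-treatment to 4-week follow-up will be examined using paired t-tests". It continues: "Effect sizes will be computed for the intervention and control arms using Hedges" g_av, with confidence intervals. The Statistical Considerations paragraph says Aim 2 looks at distributions of change "rather than testing statistical significance" and that the pilot is not meant to support efficacy conclusions.

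**The concern.** Whether an effect lasts to A3 can be asked in two ways: is the patient still better than at the start, and is the intervention arm still better than control? The A2-A3 change answers neither. It describes movement after treatment ended. A near-zero A2-A3 change is compatible with a kept gain, with no gain to begin with, or with a loss the test was too small to see. Being within-arm, it also cannot separate a lasting effect from the course of advanced disease. The control arm is randomised and measured at A3, but no named contrast uses it.

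At stake is a stated question of the pilot. Followed as written, the plan yields no interval for the effect at follow-up relative to baseline or to control. Because no criterion is given, a non-significant A2-A3 test could be reported as maintenance. The follow-up estimate is also something the later, larger trial would want.

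**Working it through.** **Inputs from the documents.** N=40, allocated 24 to 16; 20% attrition; intervention n=19 after attrition; d=0.5; two-sided alpha 0.05; about 80% power.

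**Assumptions.** The documents give no SD and no within-person correlation r, so SD=1 and r=0.5 or 0.73. All 19 are taken to be evaluable at A3. Control n=13 at A3 is 0.8 × 16 = 12.8, rounded; it is not stated.

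**The plan's own figure.** A paired t-test with n=19 and d_z=0.5 (in SD-of-change units) has 54% power by the noncentral t distribution, df=18. Reaching 80% needs d_z=0.680. Since d_z = d_av / sqrt(2(1−r)), d_av=0.5 gives 0.680 when r=0.73. That is where the second value of r comes from. It is the correlation that would make the plan's figure true, not one the plan states. The power statement is a separate matter and the present point does not depend on it.

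**How often the A2-A3 test misses a real loss.** SD of change / SD of outcome = sqrt(2(1−r)), which is 1.00 at r=0.5 and 0.735 at r=0.73. Suppose a gain of 0.5 SD at A2.

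| Loss by A3 | d_z, r=0.5 | Non-significant | d_z, r=0.73 | Non-significant |
|---|---|---|---|---|
| All (0.50 SD) | 0.50 | 46% | 0.68 | 20% |
| Half (0.25 SD) | 0.25 | 82% | 0.34 | 71% |

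**How often the misleading pattern appears.** The pattern is a significant A1-A2 gain followed by a non-significant A2-A3 change. In 200,000 simulated trials per case, with all three correlations equal:

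| Loss by A3 | r=0.5 | r=0.73 |
|---|---|---|
| All | 17% | 12% |
| Half | 40% | 53% |

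**Why the planned outputs cannot be added up.** Among people with all three assessments, the mean A1-A3 change is the sum of the two planned means. Its variance is Var(A2−A1) + Var(A3−A2) + 2Cov, and the covariance is not a planned output. With SD=1 and equal correlations, each segment has variance 2(1−r) and the covariance is −(1−r). The true variance is therefore 2(1−r), against 4(1−r) if the covariance is ignored, so the SD is overstated by a factor of sqrt(2), or 41%. With adjacent r=0.73 and A1-A3 r=0.53 the ratio is sqrt(4 × 0.27 / (2 × 0.47)) = 1.07, or 7%. If anyone drops out between A2 and A3, the two planned means come from different people and even the sum fails.

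**Precision of the added estimates (95% CI half-widths).**
- A1-A3 change, intervention arm: t(0.975, 18)/sqrt(19) = 2.101/4.359 = 0.48 SD of change. At r=0.73 this is 0.482 × 0.735 = 0.35 SD of the outcome.
- A3 difference between arms, unadjusted: t(0.975, 30) × sqrt(1/19 + 1/13) = 2.042 × 0.360 = 0.74 SD.
- The same, adjusted for baseline and stratum: t(0.975, 28) × 0.360 × sqrt(1−r²) = 0.64 SD at r=0.5 and 0.50 SD at r=0.73.

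**The case against.** The strongest reply is that the miss rates measure a misreading the plan never commits to. It plays down significance testing and says confidence intervals will be examined. A careful reader of a wide A2-A3 interval would see that loss is not excluded. That stands, and it is why this is an improvement rather than an error. It does not supply the missing estimate, because even a well-read A2-A3 interval says nothing about A3 against baseline or control.

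A second reply is that the effect sizes are tied to arms and not to intervals, so an A1-A3 g_av is not excluded. True, but it is not named either, and one sentence would settle it.

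A third is that the added estimates are weak. With half the gain kept, the A1-A3 interval in the intervention arm would exclude zero in only about 18% (r=0.5) or 29% (r=0.73) of trials. The between-arm half-width is at least as large as the 0.5 effect in the power statement. This also stands. The change improves what is estimated, not how precisely, and the result would be rough input for a later trial.

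Finally, the plan names no between-arm contrast at A2 either, and separate arm estimates may be a deliberate pilot choice. But H3 is a comparative statement, so the wider gap adds to the point. Reporting a difference with its interval does not turn the pilot into an efficacy test.

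**Conclusion.** The concern holds. The plan commits to examining sustainability and states a comparative hypothesis, but its only analysis text gives no A1-A3 change, no A3 difference between arms and no rule for judging sustainability.

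The practical size is moderate. If the A2-A3 test were used as the criterion, it would miss complete loss of a 0.5 SD gain 20% to 46% of the time and half loss 71% to 82% of the time. Those figures rest on 19 evaluable patients at A3 and on assumed correlations of 0.73 and 0.5, and they matter only if non-significance is read as maintenance. The absence of a direct follow-up estimate needs none of these assumptions. Feasibility and acceptability are untouched. The change should be made because it answers a stated question at almost no cost.

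**What to change.** Add to the Aim 2 analysis:

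1. The A1-A3 change in each arm, with Hedges' g_av and a 95% CI.
2. The between-arm difference at A3, adjusted for baseline score and age stratum, with a 95% CI. The same sentence can cover A2, where no between-arm estimate is named either.
3. A statement that sustainability will be judged from these estimates and intervals, not from a non-significant A2-A3 test, and that they are descriptive and imprecise at this sample size. Keep the A2-A3 change as a descriptive estimate with its interval.

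The cost is two or three sentences. No new participants, visits or measures are needed: outcomes are already taken at A1 and A3, and the stratum is known at randomisation. One check is needed first. The Study Measures text says the FACIT-SP-12 is given at every assessment, but the questionnaire timing table does not list it, so its collection at A3 should be confirmed.
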